6.3 Pharmacokinetics

No PK assessment involved.

7 STATISTICAL METHODOLOGY

7.1 General Considerations

No inferential statistical analyses will be conducted. Descriptive statistics including the number of subjects (n), mean, standard deviation (SD), median, minimum and maximum will be used to summarize continuous variables. Number (n) and percentage (%) of subjects in each category will be used to summarize categorical variables. All data processing, summarization, and analyses will be performed using SAS® Version 9.1 or higher on Unix. Specifications for table, graphs and data listing formats can be found in the TLF specifications for this study.

7.2 Study Population

7.2.1 Disposition of Subjects

The subject disposition will be summarized and presented for the safety analysis set (SAF):

- Number and percentage of subjects enrolled in study;
- Number and percentage of subjects who stayed on study medication for the complete duration of the study* or discontinued from the study by reason of discontinuation.

*this extension study is open ended in the sense that no maximum duration is defined.

The study will end when all subjects on medication have discontinued treatment or the sponsor makes the decision to terminate the study.

7.2.2 Protocol Deviations

Protocol deviations will be assessed for all subjects allocated to treatment.

The number and percentage of subjects meeting any criteria will be summarized for each criterion and overall, by total as well as by study site. Subjects deviating from a criterion more than once will be counted once for the corresponding criterion. Any subjects who have more than one protocol deviation will be counted once in the overall summary. A data listing will be provided by site and subject.

The protocol deviation criteria will be uniquely identified in the summary table and listing.

The unique identifiers will be as follows:

- PD1 - Entered into the study even though they did not satisfy entry criteria,
- PD2 - Developed withdrawal criteria during the study and was not withdrawn,
- PD3 - Received wrong treatment or incorrect dose,
- PD4 - Received excluded concomitant treatment.

7.2.3 Demographics and Other Baseline Characteristics

Descriptive summary statistics will be produced for all parameters. For the calculation of age the initial visit of the extension study (Day 1) will be used as the reference date. For weight and BMI the data assessed at the baseline of the prior study will be used.

Demographic data and other baseline characteristics will be provided in a listing.

7.2.4 Medical History

Medical history will be coded using the Medical Dictionary for Regulatory Activities (MedDRA) and will be obtained at screening visit (see section 3.4).

Non-prostate cancer related medical history data will be summarized by presenting the number and percentage on the SAF. The summary table will be presented alphabetically by system organ class and by decreasing order of frequency of preferred terms within each system organ class.

Cancer history will be summarized by presenting the number and percentage of subjects for tumor and lymph node stages, Gleason scores, incidence of metastases and previous therapies on the FAS. The duration of prostate cancer will be calculated as (Date of first MDV3100 intake in the prior study – Date of Initial Diagnosis) + 1. Descriptive statistics will be used to summarize the duration of disease.

A listing of medical history will be provided.

7.2.5 Concomitant Medications

Concomitant medications (prescription, over-the-counter, and nutritional supplements) will be coded using the World Health Organization (WHO) drug dictionary and will be summarized by preferred WHO name and reported term. Medications will be counted by the number of subjects who took each medication. A subject taking the same medication multiple

times will only be counted once for that medication. Medications will be presented in decreasing order of frequency based on the total number of subjects who took each medication.

All concomitant medication data will be provided in a listing.

Concomitant medications are those medications or therapies with at least one dose taken between the date of first MDV3100 intake in the 121 study (inclusive) and the date of last MDV3100 dose (inclusive) and up to the end of the study.

7.3 Study Drug

Duration of treatment and total dose will be summarized in two ways:

- Descriptive statistics of MDV3100 exposure in Days
- Exposure time will be categorized according to the following categories:
 - <2 months
 - $\geq 2 - <6$ months*
 - $\geq 6 - <12$ months*
 - ≥ 12 months

*The following convention will be applied: 2 months = 60 days; 6 months = 180 days and 12 months = 365 days.

Counts and percentage of subjects in each of these categories will be summarized.

The duration of exposure (number of days) to study medication will be summarized using descriptive statistics on the SAF, where the duration of exposure to MDV3100 is defined as the last known date that subject took MDV3100 during this study – the first dose date in this study + 1 day. Dose interruptions will be ignored in the calculation.

Also a summary of average daily dose during the extension period will be provided. The daily dose received by a subject is collected for each CRF visit. Changes in dose are also collected. The daily dose will be assumed the same between 2 CRF visits if no change in dose is recorded.

In addition information on MDV3100 compliance will be summarized via descriptive statistics and via categories ($<80\%$, $\geq 80\%$). Percentage compliance is defined as the total number of capsules taken divided by the total number of capsules that should have been taken:

$$\frac{[\text{Total number of tablets consumed}]}{[(\text{'Date last dose of study drug'} - \text{'Date first dose'}) + 1] * 4] * 4} \times 100$$

where, total number of capsules consumed will be calculated as:
(total number of capsules dispensed) – (total number of capsules returned).

All study drug dosing information will be provided in a listing

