2.2 Study Design and Dose Rationale

2.2.1 Study Design

This is a multi-center phase 2, open-label extension study in prostate cancer subjects who have completed MDV3100 treatment in a prior MDV3100 study. In order to participate in this study, the subjects must have completed the prior study with MDV 3100, be in the state of at least stable disease and in the opinion of the investigator would derive benefit from continuing MDV3100 treatment. The final visit in the prior MDV3100 study, in which the subject is taking study drug, will serve as the initial visit for this extension study.

This protocol's baseline, for comparison purposes, will be considered the original baseline from the previous MDV3100 study. In addition, all ongoing concomitant medications and AEs from the previous study will be transferred onto the appropriate case report forms (eCRFs) for this study.

All subjects will take 160 mg (4 capsules) MDV3100 once daily oral dose at the same time each day. MDV3100 can be taken with or without food.

Subjects will be discontinued from study drug when continued administration of study drug is deemed to be not in the subject's best interest by the investigator based on clinical assessments. Use of other investigational drugs will also lead to discontinuation.

Throughout the study, safety and tolerability will be assessed by the recording of AEs, monitoring of vital signs and physical examinations, safety laboratory evaluations, and 12-lead electrocardiograms (ECGs).

Subjects that have not met any of the discontinuation criteria as outlined in Section 3.4 may be eligible to continue to receive treatment with enzalutamide in Study [REDACTED] upon approval and activation of this study at the participating institution. Subjects who enroll in Study [REDACTED] will not be required to have a safety follow-up visit.

Subjects who choose not to participate or are not eligible for Study [REDACTED] will complete their participation in Study 9785-CL-0121 by completing the safety follow-up visit upon activation of Study [REDACTED] at the institution.

See Section V, [Table 1](#), Schedule of Assessments for an outline of study procedures.

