5.1.2 Increase or Reduction in Dose of the Study Drugs

Subjects who experience a grade 3 or greater toxicity that cannot be ameliorated by the use of adequate medical intervention should have their treatment interrupted until the toxicity improves to a grade 2 or lower severity. Subjects may subsequently be restarted on study drug at a reduced dose with the written approval of the sponsor. An increase in dose is not permitted.

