5.1.4 Treatment Compliance

Study drug accountability will be performed to document compliance with the dosing regimen. Subjects will be asked to bring back all remaining study drug and all study drug packaging at each study visit for drug accountability.

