5.5 Adverse Events and Other Safety Aspects

5.5.1 Definition of Adverse Events (AEs)

An adverse event (AE) is defined as any untoward medical occurrence in a subject administered a study drug or has undergone study procedures and which does not necessarily have a causal relationship with this treatment. An AE can therefore be any unintended sign (including an abnormal laboratory finding), symptom, or disease temporally associated with the use of a medicinal (investigational) product, whether or not related to the medicinal (investigational) product.

An abnormality identified during a medical test (e.g., laboratory parameter, vital sign, ECG data, physical exam) should be defined as an AE only if the abnormality meets one of the following criteria:

- Induces clinical signs or symptoms
- Requires active intervention
- Requires interruption or discontinuation of study drug
- The abnormality or investigational value is clinically significant in the opinion of the investigator.

An AE observed after starting administration of the study drug is called a "treatment emergent adverse event" and usually summed up as the AEs in the clinical study report. If a diagnosis is made from the sign and/or symptom, the diagnosis should be recorded in preference to the listing of individual signs and symptoms. If not, the investigator should record each sign and symptom as an individual AE.

All AEs occurring after visit Day 1 should be recorded in the eCRF. All observed or spontaneously reported AEs will be recorded in the eCRF. Data to be recorded include a

description of the event, date and time of onset and end of the event, severity, action with respect to study drug, treatment required, relationship to study drug, and outcome of the event. All subjects who experience an AE will be followed up at appropriate time intervals until resolved or stabilized to the satisfaction of the investigator.

If an event recurs after it had resolved, it should be handled as a new AE. However, AEs that occur intermittently can be recorded as one AE. When the severity of an AE increases, the worst severity of that AE should be recorded for the entire duration.

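### SAP 7.3: the compliance formula does not compute the ratio it defines; even with a single factor of 4 it gives intake relative to full planned dose, and a second factor of 4 in the available text needs checking

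*SAP*

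**What the plan says.** SAP 7.3 (Study Drug) gives compliance in words: "Percentage compliance is defined as the total number of capsules taken divided by the total number of capsules that should have been taken". The formula follows. Its numerator is labelled in tablets, although the text around it speaks of capsules and derives consumption as capsules dispensed minus capsules returned. As the available text reads, the denominator is (last dose date − first dose date + 1) × 4 × 4. Results are to be summarised with descriptive statistics and in two categories, below 80% and 80% or above.

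The planned dose is in Protocol 2.2.1, and SAP 3.2 repeats it: "All subjects will take 160 mg (4 capsules) MDV3100 once daily oral dose at the same time each day". Protocol 4.1.1 gives the capsule strength as 40 mg.

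Protocol 5.1.2 covers departures from that dose. Subjects with severe toxicity that medical management does not resolve "should have their treatment interrupted until the toxicity improves to a grade 2 or lower severity". It continues: "Subjects may subsequently be restarted on study drug at a reduced dose with the written approval of the sponsor". It also states: "An increase in dose is not permitted". No reduced dose level is given.

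On purpose, Protocol 5.1.4 says: "Study drug accountability will be performed to document compliance with the dosing regimen". On data, SAP 7.3 says: "The daily dose received by a subject is collected for each CRF visit". It adds that dose changes are collected and that, where none is recorded, the dose is carried forward between visits.

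**The concern.** There are two separate problems with the denominator.

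The first is the multiplier. Sixteen capsules a day contradicts the planned four. If the table were programmed that way, the 80% cut would carry no information, because every subject taking the planned dose or less would fall below it.

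The second does not depend on the multiplier. With one factor of 4, the formula charges four capsules for every calendar day between first and last dose. On days when the protocol directs an interruption, or when the sponsor has approved a lower dose, fewer or no capsules are due. A subject who does exactly what is asked then scores below 100%, and the below-80% category mixes directed dose changes with missed doses.

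What is at stake is how one descriptive table is read.

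**Working it through.** **Inputs.** Planned dose 160 mg a day (Protocol 2.2.1, SAP 3.2); capsule strength 40 mg (Protocol 4.1.1); formula and 80% cut (SAP 7.3); interruption and reduction rules (Protocol 5.1.2). Let N be the number of days from first to last dose, inclusive.

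**1. Planned daily count.** 160 / 40 = 4 capsules a day.

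**2. The formula as the available text reads.**
- Denominator per day: 4 × 4 = 16.
- Exact adherence: 4N / 16N = 25.0%, for any N.
- Intake needed to reach 80%: 0.80 × 16 = 12.8 capsules a day, which is 12.8 / 4 = 3.2 times the planned dose. Protocol 5.1.2 rules out dose increases.

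**3. Bracket check.** The denominator has one opening and two closing square brackets. Deleting one `] * 4` balances it and returns 4 a day. Adding an opening bracket also balances it and keeps 16. The brackets raise doubt about the second factor but do not settle it.

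**4. Single factor of 4, directed interruption.** Take k directed days off, then a restart, with perfect intake otherwise. Compliance = 4(N − k) / 4N = 1 − k/N. This is below 80% when k > 0.20N.

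| Span N (days) | Smallest k below 80% | Score |
|---|---|---|
| 60 | 13 | 47/60 = 78.3% |
| 180 | 37 | 143/180 = 79.4% |
| 365 | 74 | 291/365 = 79.7% |
| 730 | 147 | 583/730 = 79.9% |

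Equivalently, k days off cross the cut only if N < 5k. An assumed 14-day interruption crosses only in a span under 70 days, and an assumed 28-day one only under 140 days. In a 365-day span they score 351/365 = 96.2% and 337/365 = 92.3%. Only interruptions followed by a restart count, because the span ends at the last dose.

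**5. Single factor of 4, approved reduction.** The levels here are assumptions used to show the range. At c capsules a day for d days, compliance = 1 − (4 − c)d / 4N.
- c = 3: below 80% when d > 0.80N. For 293 of 365 days: 1 − 293/1460 = 79.9%.
- c = 2: below 80% when d > 0.40N. For 147 of 365 days: 1 − 294/1460 = 79.9%.

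**6. Would the dose received work as a denominator?** Suppose a subject stops on his own initiative for 100 of 365 days. Against 4 a day he scores 265/365 = 72.6%. If the stop is recorded as a dose change and the dose received is the denominator, he scores 100%, which hides the non-adherence. If the stop is not recorded, the carry-forward rule leaves the denominator at 4 a day and the score at 72.6%. The dose received therefore cannot stand in for the dose prescribed.

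**The case against.** **The 16-a-day reading may not be in the plan.** It rests on one displayed formula taken from a PDF, and the bracket count is consistent with a duplicated fragment. The sentence above the formula and the stated four-capsule dose make the intended multiplier plain, and a program that put every adherent subject at 25% would probably be noticed. This stands: the documents support a check, not an asserted error. A reader might infer that the compliance table will be wrong for everyone, and the text does not establish that.

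**With one factor of 4, the formula can be read as the operational definition.** On that view the capsules due are the planned four a day. Protocol 5.1.1, which carries the regimen in its heading, sets 160 mg a day, and interruption and reduction sit apart in 5.1.2. This is a fair reading, and it lowers confidence that the mismatch was unintended. It does not remove the mismatch: on a day when 5.1.2 directs interruption, four capsules are not due in the ordinary sense of the definition. The statement in SAP 7.3 that interruptions are ignored closes the paragraph on exposure duration and is not made for compliance. If it were extended to compliance, the label would still need to change.

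**Other outputs show dose changes.** SAP 7.3 reports average daily dose and lists dosing information. SAP 7.5.1 summarises adverse events that led to a lower dose or a temporary stop. This also stands, and it is the main reason why the consequence is small.

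**Conclusion.** The formula and its verbal definition differ. With the multiplier as the available text reads, exact adherence scores 25%. Whether that multiplier is in the source is open. With a single 4, the result is intake relative to full planned dose, and a compliant subject drops below 80% once directed days off exceed 20% of the span.

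Three stronger conclusions are tempting, and the documents do not support them.
- *Many subjects are misclassified.* The documents give no frequency of interruption or reduction, and short interruptions rarely cross the cut. The number is unknown and may be small.
- *The dose due can be rebuilt from recorded dose changes.* SAP 7.3 describes the dose received, not the dose prescribed. The adverse event record ("date and time of onset and end of the event, severity, action with respect to study drug, treatment required") is not shown to say who stopped the drug or on which dates.
- *Safety conclusions are affected.* Compliance defines no endpoint, safety table or analysis set. The safety analysis set requires only one dose in this study.

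Severity is minor. The thresholds assume perfect intake apart from the directed change, and the reduced levels of 2 and 3 capsules are illustrations only.

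**What to change.** Before database lock:

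1. Check the denominator against the source SAP and the analysis program. Keep a single factor of 4 and remove the second if it is there, which also balances the brackets. Replace *tablets* with *capsules*.
2. Label the measure *percentage of full planned dose*. Add a note that the below-80% category includes directed interruptions and approved reductions, and should be read alongside average daily dose and the adverse event summaries of lowered or interrupted dosing.
3. Only if the prescribed dose and dated directed interruptions were collected, also report compliance with the sum of capsules prescribed per day as the denominator. Do not use the dose received instead, and do not infer directed interruptions from the adverse event action field alone.

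Items 1 and 2 cost one corrected formula, one table title and a note. If the program does contain the second factor, one table must be rerun. Item 3 needs additional programming for one table and depends on data that the documents do not show to exist.

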7.4 Analysis of Efficacy

Not applicable

7.5 Analysis of Safety

Safety analyses will be conducted using the SAF.

7.5.1 Adverse Events

AEs will be coded to system organ class and preferred term using the Medical Dictionary for Regulatory Authorities (MedDRA) and graded using NCI-CTCAE.

Treatment-emergent adverse events (TEAE) will be presented within each system organ class by preferred term, by relationship to study drug and by severity (NCI-CTCAE grade). AEs leading to dose reduction or temporary discontinuation of study drug, AEs leading to permanent discontinuation of study drug, SAEs, and SAEs by NCI-CTCAE grade will be summarized. AEs will also be summarized by NCI-CTCAE grade and relationship to study drug jointly.

All AEs data will be displayed in listings. In addition listings of deaths, SAEs, drug related AEs, AEs leading to dose reduction or temporary discontinuation of study drug and AEs leading to permanent discontinuation of study drug will be presented.

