3.2 Inclusion Criteria

Subject is eligible for the study if all of the following apply:

1. Institutional Review Board (IRB)-/Independent Ethics Committee (IEC)-approved written Informed Consent and privacy language as per national regulations must be obtained from the subject or legally authorized representative prior to any study-related procedures (including withdrawal of prohibited medication, if applicable).
2. Has completed a prior study with MDV3100, can be enrolled in this extension study without any interruption in study drug, and in the opinion of the investigator would derive benefit from continuing MDV3100 treatment.
3. No new clinically significant abnormalities based upon physical examination, safety laboratory data, vital signs, ECG, and other clinical assessments noted from the last visit conducted during the subject's active MDV3100 study prior to initiation of this study.
4. Male subjects and their female spouses/partners who are of childbearing potential must be using highly effective contraception¹ consisting of two forms of birth control (one of which must be a barrier method) starting at Screening and continue throughout the study period and for 3 months after final study drug administration. Male subjects must not donate sperm starting at Screening and throughout the study period and for at least 3 months after final study drug administration.
5. Subject agrees not to participate in another interventional study while on treatment.

¹Highly effective contraception is defined as:

- Established use of oral, injected or implanted hormonal methods of contraception.
- Placement of an intrauterine device (IUD) or intrauterine system (IUS).
- Barrier methods of contraception: Condom or occlusive cap (diaphragm or cervical/vault caps) with spermicidal form/gel/film/cream/suppository

Waivers to the inclusion criteria will **NOT** be allowed.

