3 STUDY OBJECTIVE(S), DESIGN

3.1 Study Objectives

The main objective of this study is to follow up the long-term safety of continued administration of MDV3100 in prostate cancer subjects who were enrolled and completed MDV3100 treatment period in prior (e.g., phase 1) studies.

The long-term safety will be determined by:

- Adverse Events
- Vital Signs
- 12-lead ECGs
- Physical Examination
- Safety laboratory evaluation
- ECOG performance status.

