3.2 Study Design

This is a multi-center phase 2, open-label extension study in prostate cancer subjects who have completed MDV3100 treatment in a prior study. In order to participate in this study, the subjects must have completed the prior study with MDV 3100, be in the state of at least stable disease and in the opinion of the investigator would derive benefit from continuing MDV3100 treatment. The final visit in the prior MDV3100 study, in which the subject is taking study drug, will serve as the initial visit for this extension study.

The extension protocol's baseline, for comparison purposes, will be a baseline from the prior MDV3100 study. In addition, all ongoing concomitant medications and AEs from the prior study will be transferred onto the appropriate case report forms (eCRFs) for this study.

All subjects will take 160 mg (4 capsules) MDV3100 once daily oral dose at the same time each day. MDV3100 can be taken with or without food.

Subjects will be discontinued from study drug when continued administration of study drug is deemed to be not in the subject's best interest by the investigator based on clinical assessments. Use of other investigational drugs will also lead to discontinuation.

Throughout the study, safety and tolerability will be assessed by the recording of AEs, monitoring of vital signs and physical examinations, safety laboratory evaluations, and 12-lead electrocardiograms (ECGs).

Subjects will have a safety follow-up visit 30 days after their last dose of study drug.

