3.4 Transfer of data from prior study

Relevant data from the prior study has been transcribed to the eCRF of this study. This is done on the basis of specific instructions by the Investigators involved.

Demographic information (date of birth, ethnicity, race as described by the subject and height) collected at screening of the prior study with MDV3100 has been transcribed onto the appropriate eCRF for this study.

Medical history, as well as non prostate cancer medical history that stopped at or prior to screening, recorded at screening of the prior study with MDV3100 has been transcribed onto the appropriate eCRF for this study.

Medical history and disease history of the target disease recorded at screening of the prior study with MDV3100 has been transcribed onto the appropriate eCRF for this study.

As stated earlier, in addition, all ongoing concomitant medications (including non-medication therapies) and AEs from the prior study have been transferred onto the appropriate case report forms (eCRFs) for this study.

Further details can be found in the Investigators EDC Instruction Manual (see references).

Because of the transfer of all relevant data from the prior study, the reporting of the extension study will be exclusively based on the data available in the database of this extension study. The only exception is that for a number of safety assessments (Laboratory data, Vital signs, ECG data and the ECOG scale) as baseline the last assessment before the first MDV3100 intake of the prior study will be used.

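### No adverse-event summary named in the SAP or protocol has a time or person-time dimension, and by-visit lab shift tables can leave out a worse repeat value

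*SAP*

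**What the plan says.** SAP 3.1: "The main objective of this study is to follow up the long-term safety of continued administration of MDV3100". SAP 7.2.1 adds that "this extension study is open ended in the sense that no maximum duration is defined".

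SAP 7.5.1 says TEAEs "will be presented within each system organ class by preferred term, by relationship to study drug and by severity". It also summarises SAEs and AEs leading to dose reduction, temporary discontinuation or permanent discontinuation. Protocol 7.5.1 introduces no other kind of dimension. SAP 7.1 fixes the statistic: "Number (n) and percentage (%) of subjects in each category will be used to summarize categorical variables". Neither document names an AE table by onset interval, a rate per patient-year, a time to first event or a cumulative incidence. SAP 7.1 also refers the reader elsewhere for layout: "Specifications for table, graphs and data listing formats can be found in the TLF specifications for this study".

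Labs, vital signs, ECG and ECOG are all summarised by visit (SAP 7.5.2, 7.5.4, 7.5.5, 7.7). Lab shift tables run from baseline to each visit. Where a window holds several values, SAP 7.9.2 takes the one nearest the target day, with ties going to the latest. SAP 7.7 plans a shift to the highest on-study grade for ECOG; SAP 7.5.2 plans none for labs.

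**The concern.** Subjects stay for different lengths of time, so a crude percentage rises with length of stay even when the underlying event rate is constant. It is also the same whether events fall in the first months or after the first year. For a long-term safety objective, that contrast is what a reader will look for, and AEs are the one repeatedly assessed safety measure whose summaries carry no time axis.

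The lab issue is separate and smaller. Protocol 5.4.3.1 calls for repeat liver tests within 48 to 72 hours of notification, and Protocol 5.8 allows extra draws after an abnormal result. Several values in one window are therefore foreseeable, and the selection rule ignores severity.

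**Working it through.** The documents give no event rate, follow-up distribution or sample size, so there is no stated figure to reproduce. What follows illustrates size under assumptions.

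**1. Crude incidence against length of stay.** Assumptions: constant first-event rate r, exponential leaving rate mu = ln2/median stay, and all subjects entering at study start. The cap T is the shortest span consistent with the planned period 3Q2011 to 1Q2017 (Protocol synopsis): 30 Sep 2011 to 1 Jan 2017 = 1920 days = 5.26 years.

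P = r/(r+mu) × [1 − exp(−(r+mu)T)]

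| r per 100 PY | median 0.5 y | 1 y | 2 y |
|---|---|---|---|
| 5 | 3.5% | 6.6% | 11.0% |
| 10 | 6.7% | 12.4% | 20.3% |
| 20 | 12.6% | 22.2% | 34.5% |

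If every subject adds the 30-day tail, the middle row becomes 7.5%, 13.1%, 20.9%, from 1 − (1−P)exp(−r×30/365.25). With uniform entry over 3 or 4 years (assumed), the 20.3% falls to 17.9% or 16.4%.

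**2. Same crude figure, different timing.** At median stay 1 year, solve for the rate that gives 12.4% when events occur only in the first 6 months (31.6 per 100 PY) or only after year 1 (23.5 per 100 PY). These are deliberately extreme patterns.

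| Pattern | Crude | Overall per 100 PY | % of those at risk, 0–<6 / 6–<12 / 12–<24 / ≥24 months |
|---|---|---|---|
| Constant | 12.4% | 10.0 | 4.1 / 4.1 / 6.9 / 11.7 |
| Early only | 12.4% | 10.1 | 12.4 / 0 / 0 / 0 |
| Late only | 12.4% | 9.9 | 0 / 0 / 15.3 / 24.1 |

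Per 100 PY by interval, the patterns are 10/10/10/10, 31.6/0/0/0 and 0/0/23.5/23.5. The constant pattern seems to climb in the percentage columns only because the later intervals are longer, so patient-years per interval are needed too. An overall rate corrects for duration but does not show timing.

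**3. Lab repeats.** Tabulated windows after Day 1 are 56 to 168 days wide (SAP Table 2), so a repeat a few days later normally falls in the same window. Let the scheduled lab fall d days from target, d = −7 to +7 (15 cases), with a repeat k days later. The repeat is used only if |d+k| ≤ |d|.

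- k = 2: used for d = −7 to −1, left out in 8 of 15.
- k = 3: used for d = −7 to −2, left out in 9 of 15.
- k = 7: used for d = −7 to −4, left out in 11 of 15.

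In the remaining cases the first value is dropped, even if it was the worse one. These are counts of cases, not expected frequencies.

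**The case against.** The best defence is that the plan is openly descriptive, agrees with the protocol and loses no data. A reader might infer that timing cannot be recovered at all. The documents do not support that: onset dates are collected (Protocol 5.5.1), all AEs are listed (SAP 7.5.1) and listings show original dates (SAP 7.9.1). But listings carry no denominators, so the gap in the summaries stands.

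SAP 7.3 summarises exposure in days, so a reader can approximate an overall rate as cases over n times mean exposure. In the 1-year illustration, mean stay is (1 − exp(−0.693×5.26))/0.693 = 1.405 years, giving 12.41/1.405 = 8.8 per 100 PY against a true 10.0. That is a fair approximation, but still silent on timing. Sponsor monitoring of common SAEs (Protocol 5.5.8) is surveillance, not a planned table.

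A reader might also infer that time in the extension is the only clock, since subjects enter if they "can be enrolled in this extension study without any interruption in study drug" and SAP 3.4 says "the reporting of the extension study will be exclusively based on the data available in the database of this extension study", apart from prior-study baselines. That goes too far. SAP 7.2.4 already uses the date of first MDV3100 intake in the prior study, so time since first intake can be derived. Only ongoing prior-study AEs are transferred, however, so that analysis would be left-truncated.

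The most substantive objection is that an interval table could mislead. Entry requires at least stable disease (SAP 3.2) and no new clinically significant abnormality (Protocol 3.2). A carried-over AE counts only if it worsens (SAP 6.2). Symptoms of progression are recorded as AEs (Protocol 5.5.2). Each can make late intervals look worse without any drug effect, and there is no comparator. This stands and must be stated beside the table.

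On labs, an omitted value is not hidden. It stays in the flagged listings, in the ALT/AST, bilirubin and creatinine threshold listing where it applies, and in the AE tables if clinically significant.

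**Conclusion.** The point holds as an inexpensive improvement, not as an error in any stated figure. As written, no named AE summary separates frequency from length of stay or early from late onset, and a worse repeat lab value can be absent from every shift table.

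At an assumed 10 first events per 100 patient-years, crude incidence varies about threefold (6.7% to 20.3%) over median stays of 0.5 to 2 years, and less with staggered entry. These sizes rest on assumed rates, exponential stay and simultaneous entry. Confidence is medium because the TLF specifications might already contain such tables.

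The text does not support reading a late cluster in such a table as a late drug effect.

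**What to change.** **SAP 7.5.1.** Add TEAEs, SAEs and AEs leading to discontinuation by onset interval from extension Day 1, cut at 180 and 365 days (the SAP 7.3 convention) and 730 days. Show numbers at risk and patient-years per interval. Beside n (%), give first events per 100 patient-years at risk. Time at risk runs from first extension dose to first event or the end of TEAE collection: 30 days after last dose (SAP 6.2), or last dose for subjects who transfer to the follow-on study (Protocol 5.5.7).

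Label the clock as time in the extension, because "The final visit in the prior MDV3100 study, in which the subject is taking study drug, will serve as the initial visit". If time since first MDV3100 intake is also shown, state the left truncation. State the entry-selection, worsening-only and progression-symptom caveats.

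Footnote the number of imputed onset dates, since SAP 7.9.1 moves partial start dates earlier. In a simulation with onset uniform within intervals, a missing day moved about 4% to 8% of such events to an earlier interval, and a missing month about 50% to 75%.

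**SAP 7.5.2.** Add a shift from baseline to worst on-treatment CTCAE grade using all scheduled and unscheduled values, as SAP 7.7 already does for ECOG.

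If the TLF specifications already hold these tables, cite them in the SAP.

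**Cost.** SAP text, some programming and a few tables from data already collected; no change to conduct. Late intervals will be sparse: with exp(−2mu), about 6%, 25% or 50% of subjects are on drug at 24 months for median stays of 0.5, 1 or 2 years. Uniform entry over 4 years lowers the last to 0.50 × (5.26 − 2)/4 = 41%.
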